The purpose of this study is to determine the effectiveness of the collaborative care model in Singapore in which clinical pharmacists, nurses and dietitians are active participants who collaborate with physicians in caring for patients with type 2 DM. Since type 2 DM is a cardiovascular risk equivalent, co-morbidities such as hypertension (HTN) and dyslipidaemia (DLP) will also be evaluated to assess the holistic care provided for our patients afflicted with these top chronic diseases in Singapore.

Specifically, this study aims to evaluate the long-term effectiveness and sustainability of an integrated collaborative care model comprising of a healthcare team (physician, clinical pharmacist, nurse, and/or dietitian) compared to the usual or conventional healthcare model (physician-centred care) mainly in the following outcomes (Table 2).

Types of Outcomes	Descriptions				
Clinical	• Glycated haemoglobin (HbA1c), systolic blood pressure (SBP), low density				
	lipoprotein (LDL), total cholesterol, high density lipoprotein (HDL) and fasting				
	triglyceride (TG) levels				
	 Incidence of minor and major hypoglycaemia 				
	 DM-related clinical visit and hospitalization 				
Humanistic	Health-related quality of life				
	Self-care management				
	Diabetes-related distress				
Economic	Cost effectiveness				
	Productivity				

Table 2. Outcome Measures for Proposed Study

The central hypothesis of this study is that patients with type 2 DM under the collaborative care model will have greater improvements in the clinical, humanistic and economic outcomes assessed than those under conventional care.

Data collection period:

12 March 2018 to 12 March 2020

Study Design and Methodology:

Study Design and Setting

This proposed project is a prospective, randomized controlled study to be conducted over a 12month period. This multi-centre study will be conducted in Bukit Batok and Choa Chu [name] Polyclinics.

Study Participants

Patients aged \geq 21 years with Type 2 DM (HbA1c > 7%) and polypharmacy (\geq 5 medications) will be eligible for this study. Patients with Type 1 DM or who are unable to communicate independently in English, Chinese or Malay will be excluded from this study.

Procedures

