The main clinical parameters to be collected include HbA1c, SBP, total cholesterol, LDL, HDL, and TG. These short-term surrogate markers are predictive of the development of long-term DM-related complications. In addition, total cholesterol and other lipid parameters allow for estimation of cardiovascular risk. While several laboratory measures of glycemic levels are available, HbA1c will be used in this study as it is a recommended and reliable index of mean glycemic control over three months. Other outcome measures include: 1) incidence of minor and major hypoglycemia reported by patients, 2) frequency of DM-related clinic visits (by physician, pharmacist, nurses, dietitians) as indicated on patients' appointment card and hospitalizations. Minor hypoglycemic events are defined as blood glucose of < 4.0 mmol/L or signs and symptoms with known precipitating causes such as irregular eating habits, increased daily activity or other attributes that can be modified. The minor hypoglycemic event should allow the patient to recover quickly with or without the ingestion of fast-acting glucose. Major hypoglycemic events are defined as any hypoglycemic symptoms, regardless of frequency, which require help from another person. The clinical information and laboratory values will be collected from the clinical databases available at the study sites, patient case notes, and patient self-reported questionnaires at baseline, at 6- and 12-month during the study period. Baseline laboratory values will be collected at enrolment. If values are not available at enrolment, the most recent value available within the 6 months preceding enrolment will be recorded.

Humanistic Outcomes

Health-related quality of life (HRQoL) will be assessed using Research Assistant-administered questionnaires at baseline and as close to the 6-month and 12-month follow-ups as possible. The HRQoL measures will include a generic measure, EQ-5D-5L, and a DM-specific measure, the Audit of Diabetes Dependent Quality of Life (ADDQoL), and Problem Areas in Diabetes (PAID). Self-care management capabilities of patients will be assessed by the Summary of Diabetes Self-Care Activities Measure (SDSCA).

Economic Outcomes

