The economic evaluation will be conducted from an institutional perspective. Direct healthcare costs will be estimated over 12 months. The direct costs will include physicians' consultation fees, laboratory and procedures, medication costs, DM-related hospitalization, and DM-related A&E visits.

Number of Subjects to be enrolled:

A 12-month study conducted in the United States of America involving the collaborative care model reported an effect size of 0.4.²⁰ With an allocation ratio of 1:1 into the intervention or control arms, approximately 125 patients are needed in each arm, to obtain a statistical power of 80% (two-sided Type I error rate = 0.05) and after taking into account a 20% dropout rate. As such, 250 patients will be needed to assess the effectiveness of a collaborative care model versus the usual model of care in the polyclinics.

Data source:

Clinical data will be collected from patient electronic case notes, prescription records accessed from CPSS2 and iPharm and investigation results from the electronic laboratory module in CPSS2. Humanistic data and incidence of hypoglycaemia will be elucidated through participant's self-reported questionnaires. Cost data will be obtained from the respective institution financial databases.

Data Analysis:

Descriptive analyses will be performed on all variables. The differences in the improvement of clinical and patient-reported outcomes will be examined between the two groups using the Student's t test or Wilcoxon rank-sum test as appropriate. Categorical data between the two study groups will be analyzed using the Chi-square test for independence or Fisher's exact test when expected cell size is less than 5. Pearson's product-moment correlation will be used to examine correlations between continuous variables such as HbA1c and HRQoL scores. Baseline factors that are significant in the bivariate analysis will be included in a multiple linear regression model to investigate the unique impact of the intervention on and the unique association of individual factors with each outcome score while adjusting for other covariates. The level of Type I error rate will be set at P < 0.05.

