The sum of the costs incurred will be compared between the two groups using the Wilcoxon rank-sum test as the cost data are not expected to be normally distributed. General linear models with a log-link to the gamma distribution will be used to conduct multivariate analysis of costs between the groups. Gamma distributions are well suited for cost data since it a right-

skewed distribution. A cost-effectiveness analysis will be performed in which the effectiveness is defined by reduction in HbA1c between baseline and the 12-month follow-up. The incremental cost-effectiveness ratio will be calculated in which the difference in total costs between two groups is divided by the difference in the reduction in HbA1c between the two groups. Sensitivity analysis will be conducted to evaluate the influence of uncertainties in the variables and assumptions employed on the analysis results.

Data Entry and Storage:

All research-related electronic data collected will be de-identified, coded and entered in Microsoft Excel spreadsheet that will be password-protected and will be stored together with research-related paper documents in the investigators office at the National University of Singapore Department of Pharmacy, Faculty of Science. All patient information will be kept strictly confidential, following the policies of the study institution(s) involved. For hardcopy data, they will be stored in designated locked cabinet(s) or room(s) that are accessible to authorized study personnel only. For electronic data, they will be stored on in a secured computer that is password-protected. The databases will not contain subject identifiers and the data linking subject identifiers and the subject identification codes will be stored separately. These documents will be retained for a minimum of three years after study completion or as per institutional policies.

Confidentiality of Data and patient Records:

Investigators in this study will have access to all research-related data on a need-to-know basis or as per institutional policies. Collaborators in this study will only have access to researchrelated data that has been coded and has no patient related identifier. Only the principal investigators and co-investigators or collaborators will have access to the data in the excel spreadsheet. There will not be any sharing or releasing of raw data to any other persons.

Publication:

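### Neither planned treatment-effect analysis guarantees adjustment for the outcome's own baseline value, which is already collected; fixing that covariate recovers precision at almost no cost

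*Protocol*

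**What the plan says.** The protocol's Data Analysis section gives two analyses of the treatment effect on continuous outcomes.

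- An unadjusted comparison: "The differences in the improvement of clinical and patient-reported outcomes will be examined between the two groups using the" Student's t or Wilcoxon rank-sum test, whichever suits.
- A regression built by screening: "Baseline factors that are significant in the bivariate analysis will be included in a multiple linear regression model". Its purpose is "to investigate the unique impact of the intervention on and the unique association of individual factors with each outcome score", so one model serves both to estimate the treatment effect and to look for associated factors. The section does not say whether the bivariate screen tests a factor against the outcome or against arm.

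Table 3 marks a baseline measurement for HbA1c, SBP, the lipids, EQ-5D-5L, ADDQoL, SDSCA and PAID. Clinical Outcomes confirms collection from databases, case notes and "patient self-reported questionnaires at baseline, at 6- and 12-month during the study period". Table 3 shows no baseline for clinic visits and hospitalization, costs or productivity.

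The sample size section says that a cited study "involving the collaborative care model reported an effect size of 0.4", without naming the outcome or the SD to which 0.4 refers. In the cost-effectiveness analysis, the "difference in total costs between two groups is divided by the difference in the reduction in HbA1c between the two groups".

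**The concern.** A change score subtracts the whole baseline value, in effect fixing its regression slope at 1. Unless that is the true slope, the baseline value carries information that the unadjusted test does not use. The planned regression can recover it, but only if the screen happens to admit the baseline value. Admission depends on the trial's own data, and the covariate set may differ between outcomes and time points.

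At stake are the width of the intervals around the treatment effects, including the HbA1c difference in the cost-effectiveness ratio, and a treatment-effect model that is known before the data are seen. An SAP may exist but is not at hand. That does not dispose of the point, because the protocol itself states the screening rule.

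**Working it through.** **1. The plan's own figure.** Inputs from the sample size section: standardised effect 0.4, 80% power, "two-sided Type I error rate = 0.05", 1:1 allocation, 20% dropout. The two-sample t calculation gives 99.08, so 100 evaluable per arm; 100/0.8 = 125 per arm and 250 in total, as stated. Power with 100 completers per arm is 80.4%.

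**2. Adjusted model against change score.** The protocol gives neither the baseline to follow-up correlation (ρ) nor the SDs, so both are assumed. Let k = baseline SD / follow-up SD. Then

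Var(adjusted) / Var(change) = (1 − ρ²) / (1 + k² − 2ρk).

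The denominator equals (1 − ρ²) + (k − ρ)², so the ratio never exceeds 1, and it equals 1 only when k = ρ. Example: k = 1, ρ = 0.5 gives 0.75/1.00 = 0.75, and 1 − √0.75 = 13%. With 0.4 read in change-score SDs and 100 per arm, power is that of a t test at 0.4/√ratio:

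| k | Variance ratio, ρ = 0.3 / 0.5 / 0.7 | CI narrower by | Power (change score 80.4%) |
|---|---|---|---|
| 0.7 | 0.850 / 0.949 / 1.000 | 8 / 2.6 / 0% | 86 / 82 / 80% |
| 0.8 | 0.784 / 0.893 / 0.981 | 11 / 5.5 / 1% | 89 / 85 / 81% |
| 1.0 | 0.650 / 0.750 / 0.850 | 19 / 13 / 8% | 94 / 90 / 86% |
| 1.2 | 0.529 / 0.605 / 0.671 | 27 / 22 / 18% | 97 / 95 / 93% |

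Simulation at k = 1 with 100 per arm gave variance ratios of 0.654, 0.742 and 0.858, close to the formula. If 0.4 is instead in raw SDs (k = 1, normal approximation), power for change against adjusted is 66.7 v 84.3%, 80.7 v 90.4% and 95.5 v 97.7% for ρ = 0.3, 0.5 and 0.7.

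**3. HbA1c after the entry rule.** Study Participants admits patients aged at least 21 "years with Type 2 DM (HbA1c > 7%) and polypharmacy", which cuts off the lower part of the baseline distribution. Assume normal values with equal SDs before selection. Truncation leaves the slope at ρ and reduces the baseline variance to a fraction v, so the ratio becomes (1 + ρ) / [(1 − ρ)v + 1 + ρ]. If 7% lies at the 20th percentile, v = 0.583; if at the 65th, v = 0.288.

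- v = 0.583, ρ = 0.3: 1.3/1.708 = 0.761; CI 12.8% narrower, power 89.7%.
- v = 0.288, ρ = 0.7: 1.7/1.786 = 0.952; CI 2.4% narrower, power 82.3%.

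The other combinations of these percentiles and correlations lie between.

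**4. Adjusted model against the planned regression.** Simulation: 6,000 trials per setting, the outcome's baseline plus 10 noise covariates, screen at p < 0.05. Power at k = 1:

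| ρ | Fixed baseline | Screened on outcome | Screened on arm imbalance |
|---|---|---|---|
| 0.3 | 93.7% | 92.6–92.8% | 81.6% |
| 0.5 | 90.1% | 89.8% | 81.4% |
| 0.7 | 86.3% | 85.7–85.8% | 80.0% |

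Under outcome screening at k = 1 the baseline value entered in 99 to 100% of trials. When the screen was on improvement, entry fell to 48% (k = 0.8) and 5% (k = 0.7) at ρ = 0.7, where there is almost nothing to gain. Under imbalance screening it entered in 4.4 to 5.6%. The largest gap is 93.7 − 81.6 = 12.1 points. Type I error of the screened regression taken alone was 4.5 to 5.4% (outcome) and 4.1 to 5.2% (imbalance).

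**5. Adjusted model against Wilcoxon on change.** Two simulations with assumed distributions at ρ = 0.7 are relevant. With heavy-tailed errors (t, 3 df), Wilcoxon had 93% and 95% power where the raw-scale adjusted model had 88% and 87%. With strong lognormal skew the two tied (68 v 68%; 78 v 77%). Rank-based ANCOVA, examined in one of the simulations, matched or beat Wilcoxon in every setting.

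**The case against.** The strongest reply is that nothing here is an error. The plan reaches its 80% power with a valid test, and a regression is already planned. Because that regression also looks for factors associated with each outcome score, screening against the outcome is the more natural reading, and on that reading it is already close to the proposed model. This stands, and it limits the point to efficiency and prespecification. It does not remove the point: the screen is undefined, and adjustment for baseline remains a result of the data instead of a decision.

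Three stronger readings are tempting and not supported.

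- A reader might infer that screening inflates type I error or that 250 patients is wrong. The simulated error rates stay near 5%, and the sample size reproduces.
- A reader might carry the 8 to 19% over to HbA1c. The entry rule narrows its baseline distribution, and 2 to 13% is the relevant range under the stated assumptions.
- A reader might infer that a linear model on the raw scale is at least as precise as anything in the plan. That holds, in large samples, against the change-score t test. It fails against the Wilcoxon option for some heavy-tailed outcomes, and the protocol's allowance for non-normal data should not be lost.

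**Conclusion.** The concern holds as one of forgone precision and a data-driven covariate rule in a treatment-effect model. Against the change-score t test the adjusted model cannot lose asymptotically, and its cost is one degree of freedom among about 200 completers. The gain runs from none (k = 0.7, ρ = 0.7) to 19% at equal SDs (ρ = 0.3), and to 27% if the baseline SD exceeds the follow-up SD by a fifth. Against the planned regression it is about one power point or less on the natural reading of the screen, and 6 to 12 points at equal SDs only if covariates are chosen by arm imbalance.

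All sizes rest on assumed correlations, SD ratios and distributions, and the power figures on reading 0.4 in change-score SDs. The sponsor should make the change because it is inexpensive and settles the model in advance; the existing plan is not invalid without it.

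**What to change.** Amend the Data Analysis section as follows.

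- For each continuous outcome with a baseline in Table 3 (HbA1c, SBP, lipids, EQ-5D-5L, ADDQoL, SDSCA, PAID), make the main treatment-effect analysis a linear model of the 12-month value on arm and that outcome's baseline value, both fixed in advance. Report the adjusted mean difference with its 95% CI, and use the same form at 6 months.
- For outcomes expected to be skewed or heavy-tailed, such as TG and some questionnaire scores, name in advance a baseline-adjusted log-scale or rank-based ANCOVA. The choice must not be made from the treatment comparison.
- Remove significance screening from the treatment-effect model. Keep the t/Wilcoxon test of improvement as a sensitivity analysis, and the screened regression only as an exploratory look at associated factors.
- Leave the planned methods for hypoglycaemia incidence and for outcomes without a baseline (visits and hospitalization, costs, productivity) as they are.
- The HbA1c difference in the cost-effectiveness ratio may be taken from the adjusted untransformed model. With baseline in the model, the arm coefficient for the 12-month value equals that for the reduction apart from sign, so the definition of effectiveness does not change.

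The cost is wording only: no extra patients, visits or measurements.

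### Screening baseline factors by significance and testing them again on the same data leaves the selected factors' P values and intervals uncalibrated; separately, the many factor tests at 0.05 need an exploratory label

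*Protocol*

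**What the plan says.** All of this is in the Data Analysis section of the protocol.

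- Selection rule: "Baseline factors that are significant in the bivariate analysis will be included in a multiple linear regression model".
- The model has two purposes. It is to investigate "the unique impact of the intervention on and the unique association of individual factors with each outcome score while adjusting for other covariates". Factor associations are therefore a declared target, alongside the treatment effect.
- Threshold, stated once for everything: "The level of Type I error rate will be set at P < 0.05".
- A further layer of association tests: "Pearson's product-moment correlation will be used to examine correlations between continuous variables such as HbA1c and HRQoL scores".

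The section does not list the candidate factors. It does not say whether the bivariate analysis sets a factor against the outcome or against the study group. The between-group comparison itself is a separate t test or Wilcoxon rank-sum test.

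**The concern.** A coefficient that is tested only because its factor already reached P < 0.05 against the same outcome, in the same patients, is not an ordinary 5% test. Factors enter because their observed association is large, partly by chance, and the second P value and interval take no account of that. A reader would take a reported independent association, with its 95% interval, at face value.

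A second, distinct matter is the number of tests. The procedure runs over every baseline factor and every outcome score, with correlations added, under a single 0.05 statement. Some associations will reach that threshold by chance whether or not there is a screen.

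At stake are the statements about which patient characteristics go with better or worse outcomes. These are non-randomised associations, secondary to the comparison of the two care models.

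**Working it through.** **Inputs from the protocol**
- Sample size (Number of Subjects to be enrolled): effect size 0.4, 80% power, two-sided 0.05, 20% dropout, 125 per arm.
- Outcomes: six continuous clinical parameters (Clinical Outcomes) and four questionnaires (Humanistic Outcomes), so M = 10. If an outcome score means a questionnaire only, M = 4.
- Candidate factors: Data Collection names demographics, medical history and medication use, without a count. K = 5 to 20 is an assumption, and so are all correlations.

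**Step 1. Reproduce the plan's own figure.** n per arm = 2(1.96 + 0.84)² / 0.4² = 98 to 99 after rounding up; 99 / 0.8 = 124 after dropout. The protocol's 125 is reproduced. Completers: 250 × 0.8 = 200, the size used below.

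**Step 2. Calibration of selected factors.** In each simulated trial every factor is screened at P < 0.05 against the outcome. Those that pass are fitted by linear regression with the treatment indicator. With 10 factors and no true association:

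| Correlation between factors | 0 | 0.3 | 0.5 |
|---|---|---|---|
| Screened-in null factor significant again | 89% | 57% | 36% |
| Implied 95% interval coverage (1 minus the row above) | 11% | 43% | 64% |
| Coverage in a separate simulation | 9% | 44% | 67% |
| Coverage with a fixed list | 95% | 95% | 95% |

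The size depends heavily on the setting. With true predictors present, coverage for selected factors ran from 61% to 98%. With two true predictors among 10 factors, a screened-in null factor was significant again in 67% of cases if factors were uncorrelated and in 2.4% if they were correlated at 0.3. The error can therefore go in either direction; the constant is that the nominal 95% is not what the procedure delivers.

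**Step 3. Does the screen create more false factors?** Same setting (10 null factors, 10 outcomes correlated 0.3), with the screen against fitting all 10:

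| Correlation between factors | 0 | 0.3 | 0.5 |
|---|---|---|---|
| False positives per candidate, screen | 4.5% | 2.8% | 1.8% |
| False positives per candidate, all fitted | 5.0% | 5.0% | 5.0% |
| Any false factor in one outcome, screen | 37% | 27% | 18% |
| Any false factor in one outcome, all fitted | 39% | 38% | 38% |
| Any false factor over 10 outcomes, screen | 97% | 95% | 83% |
| Any false factor over 10 outcomes, all fitted | 97% | 98% | 99% |

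It does not. With null factors, each must pass two tests, so the screen lowers the counts. (Other runs of the screened procedure gave 99%, 96% and 87% in the fifth row; the differences are simulation noise.)

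**Step 4. Multiplicity.** For independent null tests, the chance of at least one false association is 1 − 0.95^(K × M):
- K = 10, M = 1: 1 − 0.95^10 = 40%. Over K = 5 to 20 the range is 23% to 64%.
- K = 5, M = 10: 1 − 0.95^50 = 92%.
- K = 10, M = 10: 1 − 0.95^100 = 99.4%.
- K = 5, M = 4: 1 − 0.95^20 = 64%.
- K = 10, M = 4: 1 − 0.95^40 = 87%.

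Simulated over 10 outcomes with the screen: 73% (K = 5) to 96% (K = 15) with correlated factors and outcomes and no true predictor. With K = 10 and two true predictors it was 92% (uncorrelated) or 56% (correlated).

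**Step 5. Treatment effect.** After screening, the type I error of the treatment coefficient was 4.5% to 5.5% in the scenarios with six or more outcomes.

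**The case against.** A reader might infer that the screen makes false predictors nearly certain. The documents do not support this. Step 3 shows that the screen reduces the number of false factors when none is real, and the per-candidate error stayed at or below 5% in every simulated setting. The high figure over 10 outcomes is plain multiplicity, and its level rests on a factor count that the protocol does not give. Likely is supported; nearly certain holds only for about 10 or more largely independent factors over 10 outcomes.

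A reader might also infer that the trial's main conclusion is at risk. It is not. The aims and central hypothesis concern collaborative against usual care, that comparison has its own test, and the adjusted treatment coefficient keeps its error rate.

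Three further objections deserve weight.
- The bivariate analysis could mean factor against study group, since the preceding sentences include between-group tests. Selection would then not be on the outcome, and the coverage figures of Step 2 would not apply. The outcome reading is more natural, because the rule follows the correlation sentence and serves "the unique association of individual factors with each outcome score while adjusting for other covariates". The multiplicity point remains under both readings.
- The model is only said to investigate these associations, with no factor hypothesis and no power claimed for one. That is true and lowers the severity.
- Labels and corrections for secondary associations are often left to a statistical analysis plan, which is not shown here, so their absence alone is no finding. The screening rule, however, is fixed in the protocol, and an analysis plan that followed it would inherit the problem.

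**Conclusion.** The point holds, at low severity. On the factor-against-outcome reading, the protocol prescribes a procedure whose P values and intervals for selected factors are not calibrated: coverage from about 9% to about 98% where 95% is stated, with 200 completers and 10 assumed factors. Where in that range the trial would fall depends on how many factors truly matter and how they are correlated, neither of which the protocol gives.

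Separately, testing many factors over about 10 outcomes at 0.05 makes at least one false association likely, from about 56% to over 99% under the assumptions shown. The cause is the number of tests, not the screen. Only the secondary factor associations are affected.

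**What to change.** In Data Analysis:

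1. Replace the significance screen with one named covariate list, set without reference to the outcome data and before the unblinded analysis. Use it for all outcomes and keep every listed factor whatever its P value. This restores interval coverage and removes the ambiguity over what bivariate means. It does not by itself reduce the number of false positives; Step 3 shows as many or slightly more.
2. To deal with multiplicity, state that factor-outcome associations and Pearson correlations are exploratory, reported as estimates with 95% confidence intervals, and that no factor will be claimed as an independent predictor on P < 0.05. Reserve the 0.05 statement for the randomised comparison.

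If formal factor claims are wanted after all, control the error over the full fixed set of tests. For example, with K = 10 and M = 10, 0.05 / 100 = 0.0005 per test gives 1 − 0.9995^100 = 4.9% overall if the tests are independent.

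The cost is two or three sentences, with no new data or patients. A few degrees of freedom out of about 200 are used, and factor associations can no longer be reported as confirmed.

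### Total costs are to be compared with a rank-sum test, which does not address the mean cost difference that the cost-effectiveness ratio uses

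*Protocol*

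**What the plan says.** The Data Analysis section of the protocol makes three statements about costs.

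- The two-group comparison: "The sum of the costs incurred will be compared between the two groups using the Wilcoxon rank-sum test", with the reason "as the cost data are not expected to be normally distributed".
- The multivariable analysis: "General linear models with a log-link to the gamma distribution will be used to conduct multivariate analysis of costs between the groups".
- The ICER, in which "the difference in total costs between two groups is divided by the difference in the reduction in HbA1c between the two groups".

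The Economic Outcomes section adds: "The economic evaluation will be conducted from an institutional perspective". It lists the direct costs over 12 months as physician fees, laboratory work and procedures, medication, and diabetes-related admissions and emergency visits. The protocol names no unadjusted estimate or test of the difference in mean cost.

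**The concern.** The cost test and the ICER address different quantities. The rank-sum test asks whether a patient in one arm tends to cost more than a patient in the other. The ICER needs the amount by which average cost differs. An institution's spend is mean cost times number of patients, so under the stated perspective the arithmetic mean is the relevant quantity. Skewness is a reason to use a robust or bootstrap interval for the mean. It is not a reason to compare something else.

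The trial could plausibly produce a divergence. The Procedures section schedules pharmacist visits every four to six weeks in the collaborative arm, which may move routine resource use modestly for many patients. Any saving from avoided admissions would fall on a few patients with large costs, and ranks discard the size of those costs.

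A reader could take the rank-sum p-value as the test of the cost difference in the ICER. The p-value may be significant while the mean difference is inconclusive, or it may miss a real mean saving.

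**Working it through.** **Sample size.** The protocol plans 125 per arm from an effect size of 0.4, 80% power, two-sided 5% and 20% dropout. The formula 2(1.960 + 0.842)²/0.4² gives 98.1, or 99 per arm after the usual rounding and small-sample adjustment. Then 99/0.8 = 123.75, or 124, which agrees with 125. Evaluable patients: 125 × 0.8 = 100 per arm.

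**Assumed costs (dollars; none are in the protocol).** Routine cost is gamma with mean 1,000 and coefficient of variation (CV) 0.5 unless stated. Each admitted patient adds a gamma cost with mean 6,000 and CV 0.5. Mean cost = routine cost + admission rate × 6,000.

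**Worked case.** Control: 1,000 + 0.12 × 6,000 = 1,720. Collaborative care, with 300 added and admissions at 6%: 1,300 + 0.06 × 6,000 = 1,660. The true mean is 60 lower, although most patients cost more.

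- Variance = routine variance + p × 6,000² × 1.25 − (p × 6,000)².
- Control: 250,000 + 5,400,000 − 518,400 = 5,131,600.
- Collaborative: 250,000 + 2,700,000 − 129,600 = 2,820,400.
- Standard error of the difference: √((5,131,600 + 2,820,400)/100) = 282. The 95% half-width is 1.96 × 282 = 553.

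**Simulation, true mean equal or lower under collaborative care.** 20,000 trials per scenario, 100 per arm, mean difference by Welch test. The last three columns are percentages of all trials.

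| Added routine cost | Admissions | True mean difference | Rank-sum: collaborative significantly dearer | Same, with mean difference not significant | Same, with mean significantly cheaper |
|---|---|---|---|---|---|
| 300 | 10% to 5% | 0 | 88.8 | 84.9 | 0.3 |
| 300 | 12% to 6% | −60 | 83.0 | 80.6 | 0.6 |
| 200 | 12% to 6% | −160 | 42.1 | 41.3 | 0.2 |
| 100 | 12% to 6% | −260 | 7.6 | 7.5 | 0.0 |
| 0 | 12% to 6% | −360 | 0.3 | 0.3 | 0 |
| 300 on routine 3,000 | 12% to 6% | −60 | 8.8 | 7.2 | 0 |
| 30% proportional, CV 0.5 | 12% to 6% | −60 | 56.3 | 54.4 | 0.1 |
| 30% proportional, CV 1.5 | 12% to 6% | −60 | 3.5 | 2.5 | 0 |

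Across all 15 such scenarios the discordant pattern occurs in 0.3% to 84.9% of trials. With a gamma log ratio in place of the Welch test, significance in opposite directions reaches at most 1.3%. In a separate run of 4,000 trials of the worked case, 43% had a significantly dearer rank-sum result beside a negative observed mean difference. That share was 20% with 200 added, 2.7% with 100 added, and under 0.1% at routine cost 3,000.

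**Saving only (nothing added, admissions down from 12%).** Percentage of trials detecting the saving:

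| Admissions fall to | True saving | Rank-sum | Mean comparison |
|---|---|---|---|
| 6% | 360 | 10.9 | 25.0 |
| 4% | 480 | 16.0 | 44.1 |
| 2% | 600 | 23.2 | 71.3 |

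Hand check of the first row: 360/282 = 1.28, and the normal probability above 1.96 − 1.28 = 0.68 is 25%.

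**Uniform rise (admissions 12% in both arms).** The rank-sum test detects it more often: 93.3% against 16.2% for 300 added, and 64.3% against 9.0% for 200 added.

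**Other distributions (4,000 trials each).** With identical gamma costs the rank-sum test rejects in 4.8% of trials and Welch in 4.9%. With equal means of 1,000 but gamma shapes 2 and 1, the figures are 27.7% and 5.4%. With shapes 2 and 0.8 they are 47.3% and 5.7%. With equal means of about 1,199, where one arm has higher routine cost and fewer admissions, they are 53.5% and 4.8%.

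**The case against.** - **The gamma model already compares mean costs.** This is correct, and it limits the point. But that model is the adjusted analysis, its log link gives a ratio of means, and the protocol does not connect it to the ICER numerator. The unadjusted comparison remains the rank-sum test.
- **No p-value enters the ICER, and its formula is not wrong.** Both statements stand. The word mean is an inference, though the only coherent reading for a per-patient ratio. The concern is how the cost comparison beside the ratio will be read.
- **The cost inputs are invented and the range is wide.** True. The upper end needs 300 added to a routine cost of 1,000 while admissions halve. The listed direct costs include no pharmacist charge, so such a rise would have to come from items such as medication or tests. With 0 to 100 added, the discordance is 0.3% to 7.5%.
- **Much of the discordance is a difference in power.** Also true. With a real uniform rise of 300, a separate run showed the same pattern in 77% of trials, and there the rank-sum direction was right. It still gives no amount.
- **Intervals and conversions belong in an SAP.** The absence of an interval is not counted here. The point rests on a test the protocol itself chooses and justifies.

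**Conclusion.** The concern holds and is minor. The stated rank-sum test does not address the quantity in the ICER, and non-normality does not justify the switch. That conclusion does not depend on the assumed costs; only its practical size does. Depending on those inputs, disagreement between the rank-sum result and the mean comparison ranges from negligible to frequent. Significant results in opposite directions are rare. The rank-sum test loses power for savings concentrated in admissions and gains power for a uniform rise. The HbA1c analysis, the sample size and the ICER point estimate are unaffected.

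**What to change.** In the Data Analysis section, replace the rank-sum comparison of costs with the difference in arithmetic mean cost per patient and a non-parametric bootstrap 95% confidence interval. Report it unadjusted, and also adjusted by turning the gamma model's arm effect into a mean difference through standardised predictions. State that the unadjusted mean difference is the ICER numerator. Drop the rank-sum test for costs, or keep it labelled as descriptive.

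This takes one or two sentences and a few lines of code, with no new data. In five assumed scenarios (400 trials each, 1,000 resamples per trial), bootstrap coverage was 93.0% to 95.8% unadjusted and 93.5% to 95.2% adjusted. In 3 to 24 of the 400 trials per scenario at least one resample fit of the gamma model had not fully converged; these trials were kept.

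There are two downsides. The interval will be wide, with a median half-width of about 520 to 730 dollars in those scenarios, so the cost result may be inconclusive. A uniform rise in routine cost would also be detected less often than by the rank-sum test.
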